10.7.2 Unblinding

At the initiation of the study, the study site will be instructed on the method for breaking the blind. The unblinding method will be either a manual or electronic process.

Unblinding of the individual subject's treatment by the investigator will be limited to medical emergencies or urgent clinical situations in which knowledge of the subject's study treatment is necessary for clinical management. In such cases, investigators will use their best judgment as to whether to unblind without first attempting to contact the medical monitor to discuss and agree to the need for unblinding. If investigators deem it not necessary to unblind immediately, they will first attempt to contact the medical monitor to discuss and agree to the need for unblinding.

If investigators have tried but are unable to reach the medical monitor, they will use their best judgment, based on the nature and urgency of the clinical situation, and may proceed with unblinding without having successfully reached and discussed the situation with the medical monitor.

Contact information for the medical monitor (or appropriate backup) will be provided in a separate document.

In addition, the Vertex Medical Information Call Center will answer calls 24 hours a day, 7 days a week, 365 days of the year, and will triage these calls to the study medical monitor or appropriate backup.

If a subject's treatment assignment has been unblinded for a medical emergency or urgent clinical situation, the medical monitor will be notified within 24 hours of the unblinding event. The reason and the date of the unblinding will be documented clearly in the subject's study file. Information about the treatment assignment obtained from the unblinding will be maintained in a secure location with controlled access and will not be shared with the sponsor (Vertex), CRO, or any site personnel (other than the physician treating the subject). In addition, the investigator will consider whether the clinical event that prompted unblinding will be considered an SAE, according to the regulatory definitions or criteria for SAEs, and if so, submit an SAE report to GPS or designee, per Section 13.1.2.

Vertex GPS or designee will also unblind any SAE reports in compliance with regulatory reporting requirements. In addition, Vertex may, for matters relating to safety concerns, unblind individual subjects at any time.

11 ASSESSMENTS

11.1 Timing of Assessments

The timing of assessments is shown in Table 3-1 and Table 3-2.

11.2 Subject and Disease Characteristics

Subject and disease characteristics include the following: demographics, medical history, height, and weight.

11.3 Pharmacokinetics

11.3.1 Blood Sampling

For the evaluation of plasma concentrations of VRT-1207355 and VRT-1268114, blood samples will be collected from all subjects according to the Schedule of Assessments (Table 3-2).

These samples may also be used for evaluations of VX-150, metabolites of VRT-1207355, for further evaluation of the bioanalytical method, and for analyses that provide information on the metabolic pathways used by or affected by VX-150 and VRT-1207355.

Blood samples collected from subjects administered placebo will not be routinely analyzed.

[figure not shown]
The following will be recorded before PK sample collection: date and time the dose was taken, amount taken, time since they last ate, and a description of the contents of their meal.

11.3.2 Processing and Handling of Pharmacokinetic Samples

Detailed procedures for the collection of blood samples and further procedures for processing and handling of samples for PK analysis will be provided in the PK sample handling guidelines. The shipment address and assay laboratory contact information will be provided to the investigational site before initiation of the study.

11.3.3 Bioanalysis

Samples will be analyzed using a validated analytical method in compliance with Vertex or designee standard operating procedures. A description of the assay and validation data will be provided in separate reports.

11.5 Efficacy

11-point NRS: Pain intensity will be evaluated using the 11-point NRS. From Day -7 through Week 6, subjects will report their average daily pain during the last 24 hours on the NRS via electronic diary.

At study visits, subjects will also report their average pain during the last 24 hours on the NRS. The NRS scores from the daily diary will be used in the primary endpoint analysis, and the proportion of subjects with $\geq 30\%$ and $\geq 50\%$ reduction in weekly average scores as reported in the daily diary and at study visits will be used in the secondary endpoint analyses.

DSIS: The DSIS will be completed each morning in an electronic diary to describe how pain interfered with the subject's sleep.

PGIC: The PGIC will be completed at study visits to quantify the change in subjects' overall status

11.6 Safety

Safety evaluations will include AEs, clinical laboratory assessments, clinical evaluation of vital signs, ECGs, physical examinations (PEs), and the C-SSRS.

11.6.1 Adverse Events

All AEs will be assessed, documented, and reported in accordance with ICH GCP guidelines. Section 13.1 outlines the definitions, collection periods, criteria, and procedures for documenting, grading, and reporting AEs. A separate document that details AE CRF completion guidelines for investigators as well as training will be provided.

11.6.2 Clinical Laboratory Assessments

At the Screening Visit, blood specimens will be collected for safety laboratory tests following at least a 4-hour fast. At other time points, fasting is only required with respect to dosing (see Section 9.4.2 and Section 9.5). On Day 1, blood samples will be collected before the first dose of study drug. At all other scheduled visits, these samples will be collected at any time during the clinic visit.

Blood and urine samples for clinical laboratory assessments will be collected as shown in Table 3-1 and Table 3-2. Laboratory test results that are abnormal and considered clinically significant will be reported as AEs (see Section 13.1).

The safety laboratory test panels are shown in Table 11-1.

Table 11-1 Safety Laboratory Test Panels

Serum Chemistry	Hematology	Urinalysis ^a
Glucose	Hemoglobin	Leukocyte esterase
Blood urea nitrogen ^b	Erythrocytes	Nitrite
Creatinine	Mean corpuscular volume	Urine protein
Sodium	Platelets	рН
Potassium	Leukocytes	Urine blood
Calcium	Differential (absolute and percent):	Specific gravity
Chloride	Eosinophils	Urine glucose
Magnesium	Basophils	
Bicarbonate	Neutrophils	
Phosphate	Lymphocytes	
Bilirubin, direct bilirubin	Monocytes	_
Alkaline phosphatase	Coagulation	
Aspartate transaminase (=SGOT)	Activated partial thromboplastin time	-
Alanine transaminase (=SGPT)	Prothrombin time	
Gamma-glutamyl transferase	Prothrombin time International	
Protein	Normalized Ratio	
Albumin		
Creatine kinase		
Thyrotropin		
Cholesterol		
Triglycerides		
Low-density lipoprotein-direct		
High-density lipoprotein		

Note: Screening Visit blood draws will be done after a minimum 4-hour fast.

^a If urinalysis results are positive for leukocyte esterase, nitrite, protein, or blood, microscopic examination of urine will be performed and results provided for leukocytes, erythrocytes, crystals, bacteria, and casts.

b If blood urea nitrogen cannot be collected, urea may be substituted.

Additional tests at screening: The following additional tests will be performed during screening to assess eligibility:

- Serum beta-human chorionic gonadotropin (β -hCG) for all female subjects
- Serum follicle-stimulating hormone (FSH) for suspected postmenopausal female subjects only. Levels will be within the laboratory's range for postmenopausal levels for subjects to be considered of non-childbearing potential.
- Serology includes testing for hepatitis B surface antigen (HBsAg) and antibodies to hepatitis C virus (HCV) and human immunodeficiency viruses 1 and 2 (HIV 1/HIV 2).
- HbA1c (for subjects with diabetes only)
- Thyroid function test
- Methylmalonic acid
- Vitamin B12

Clinical laboratory assessments from screening will have no clinically significant findings that preclude participation in the study, as judged by the investigator, for a subject to receive study drug on Day 1.

Pregnancy testing for female subjects of childbearing potential (as defined in Section 11.6.6.1):

Pregnancy test results must be negative for female subjects of childbearing potential to receive study drug.

During treatment, if a urine or serum pregnancy test is positive, all study drug dosing will stop and the pregnancy will be confirmed with a serum β -hCG test. If confirmed, the pregnancy will be reported and the subject will be permanently withdrawn from study drug dosing as discussed in Section 11.6.6.2. If a pregnancy test is positive, the procedures outlined in Section 11.6.6.2 will be followed.

Drug and alcohol testing: Opiates, methadone, amphetamines/methamphetamines, cannabinoids, cocaine, barbiturates, and benzodiazepines will be assessed by a urine test. Alcohol will be assessed by a blood, urine, or breath test. Subjects may undergo random drug and alcohol testing if deemed appropriate by the investigator. Drug and alcohol test results must be negative for all subjects to receive study drug.

Additional Evaluations: Additional clinical laboratory evaluations will be performed at other times if judged to be clinically appropriate.

For purposes of study conduct, only laboratory tests done in the central laboratory may be used. Local laboratories may be used at the discretion of the local investigator for management of urgent medical issues. If a local laboratory test value is found to be abnormal and clinically significant, it will be verified by the central laboratory as soon as possible after the investigator becomes aware of the abnormal result. If it is not possible to send a timely specimen to the central laboratory (e.g., the subject was hospitalized elsewhere), the investigator may base the assessment of an AE on the local laboratory value.

11.6.3 Physical Examinations and Vital Signs

A PE of all body systems and vital signs assessment will be performed at screening and select study visits (Table 3-1 and Table 3-2). At other visits, symptom-directed PEs will occur at any time during the study if triggered by AEs or if deemed necessary by the investigator.

A PE includes a review of the following systems: head/neck/thyroid; eyes/ears/nose/throat; respiratory; cardiovascular; lymph nodes; abdomen; skin; musculoskeletal; and neurological. Breast, anorectal, and genital examinations will be performed when medically indicated. After screening, any clinically significant abnormal findings in PEs will be reported as AEs.

The neurological component of the Day 1 complete PE includes the bedside sensory testing kit (BSTK) for the purpose of standardized assessment and phenotyping of subjects' pain, using the usual components of the neurological examination. Included in the BSTK are standard tools used in assessment of the neurological system, including a turning fork, foam brushes, von Frey fiber, and safety pins.

A focused neurological examination will be performed at all other visits after the Day 1 Visit. The focused neurological examination includes: testing of strength via the Medical Research Council (MRC) rating scale, reflexes, sensation to light touch, and pin prick.

Vital signs include blood pressure (systolic and diastolic), temperature (oral), pulse rate, and respiration rate. These will be assessed following at least a 5-minute rest in the seated or supine position.

11.6.4 Electrocardiograms

Standard 12-lead ECGs will be performed using a machine with printout according to the Schedule of Assessments (Table 3-1 and Table 3-2). Additional standard 12-lead ECGs will be performed at any other time if clinically indicated. The performance of all ECGs will adhere to the following guidelines:

- The subject will be instructed to rest in the supine position for at least 5 minutes before having an ECG performed.
- The ECG will be performed before any procedures that may affect heart rate, such as blood sampling.

The ECG traces will be manually read at the study site at the Screening Visit and Safety Follow-up Visit. A printout of the ECG traces will be made for safety review by the investigator and maintained with source documentation. Clinically significant ECG abnormalities occurring during the study through the Safety Follow-up Visit will be recorded as AEs.

To ensure safety of the subjects, a qualified individual at the study site will make comparisons to baseline measurements. If the QTcF is increased by >60 msec from the baseline or an absolute QTcF value is ≥500 msec for any scheduled ECG, 2 additional ECGs will be performed approximately 2 to 4 minutes apart to confirm the original measurement. If either of the QTcF values from these repeated ECGs remains above the threshold value (>60 msec from baseline or ≥500 msec), a single ECG will be repeated at least hourly until QTcF values from 2 successive ECGs fall below the threshold value that triggered the repeat measurement. A subject with a QTcF value above the threshold value will discontinue dosing.

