9 STATISTICAL ANALYSIS

9.1 General Considerations

The Schedule of Assessments is provided in Section 3 of CSP. The precision standards for reporting safety and efficacy variables are provided in an internal Biometrics document that specifies the programming rules including the precision for derived variables.

All individual subject data, including those derived, for subjects who were randomized or received at least 1 dose of study drug, i.e. All Subjects Set, will be presented in individual subject data listings as described.

Continuous variables will be summarized using the following descriptive summary statistics: the number of subjects (n), mean, standard deviation (SD), standard error (SE), median, minimum value (min), and maximum value (max).

Categorical variables will be summarized using counts and percentages.

Baseline value for the NRS via daily diary and the DSIS will be defined as the average score of at least 4 nonmissing scores from Day -7 to Day -1. For all other variables baseline will be defined as the most recent nonmissing measurement collected before the initial administration of study drug unless specified otherwise.

Change (absolute change) from baseline will be calculated as post-baseline value – baseline value unless otherwise specified.

Treatment-emergent (TE) Period will be defined as the time from dosing with study drug until the following time point:

- For enrolled subjects who have a Safety Follow-up Visit: through the Safety Follow-up Visit
- For enrolled subjects who do not have a Safety Follow-up Visit, the earliest of
 - 35 days after the last dose of study drug, or
 - the ETT Visit if that visit is 3 weeks or later following the last dose of study drug (see Section 9.1.5 of CSP)

Unscheduled visits: Unscheduled visit measurements will be included in analysis as follows:

- In scheduled visit windows per specified visit windowing rules.
- In the derivation of baseline/last on-treatment measurements.
- In the derivation of maximum/minimum on-treatment values and maximum/minimum change from baseline values for safety analyses.
- In individual subject data listings as appropriate.

Visit windowing rules: The analysis visit windows for protocol-defined visits are provided in [Appendix A](#).

Incomplete/missing data will not be imputed, unless otherwise specified.

Outliers: No formal statistical analyses will be performed to detect or remedy the presence of statistical outliers, unless specified otherwise.

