9.4.3 Electrocardiogram

A summary of raw values and change from baseline values will be provided by treatment at each scheduled visit during the TE period for the following standard 12-lead ECG measurements: PR, QT, QRS, QTcF [QTcF = QT/RR^{0.33}], and HR. In addition, the number and percentage of subjects by maximum on-treatment value of QT/QTcF intervals, categorized as \leq 450 msec, $>$ 450 msec and \leq 480 msec, $>$ 480 msec and \leq 500 msec, and $>$ 500 msec, as well as maximum on-treatment change from baseline value of QT/QTcF intervals, categorized as \leq 0 msec, $>$ 0 and \leq 30 msec, $>$ 30 and \leq 60 msec, and $>$ 60 msec, will be provided.

The threshold value criteria for ECG data are provided in [Appendix D](#). A listing containing individual subject measurements meeting the threshold value criteria at any visit will be provided. For each subject in the listing, ECG measurements at all visits will be included.

Clinically significant ECG abnormalities occurring during the study through the Safety Follow-up Visit will be recorded as AEs.

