12 LIST OF APPENDICES

Appendix A: Analysis Visit Windows for Safety and Efficacy Assessments

Table 12-1 Analysis Visit Windows for Safety and Efficacy Assessments

Assessment	Visit ¹	Target Study Day per the protocol	Analysis Visit Window (in study days)
Safety Assessment			
Hematology	Baseline	1	[Screening visit, Pre-dose Day 1]
Serum Chemistry	Week 3	22	[1*, 32]
	Week 6	43	[33, 57]
	Safety Follow-up Visit	N/A	Nominal
Coagulation	Baseline	N/A	[Screening visit, Pre-dose Day 1]
	Week 6	43	[1*, 57]
	Safety Follow-up Visit	N/A	Nominal
Standard 12-Lead ECG	Baseline	1	[Screening visit, Pre-dose Day 1]
	Day 7	7	[1*, 57]
	Safety Follow-up Visit	N/A	Nominal
Vital Sign	Baseline	1	1
	Day 7	7	[2, 14]
	Week 3	22	[15, 32]
	Week 6	43	[33, 57]
	Safety Follow-up Visit	N/A	Nominal
C-SSRS	Baseline	1	[-1, 1]
	Day 7	7	[2, 14]
	Week 3	22	[15, 32]
	Week 6	43	[33, 57]
	Safety Follow-up Visit	N/A	Nominal

Table 12-1 Analysis Visit Windows for Safety and Efficacy Assessments

Assessment	Visit ¹	Target Study Day per the protocol	Analysis Visit Window (in study days)
Efficacy Assessment			
NRS via daily diary	Baseline	N/A	[-7, -1] ²
DSIS via daily diary	Week 1	N/A	[1*, 7]
	Week 2	N/A	[8, 14]
	Week 3	N/A	[15, 21]
	Week 4	N/A	[22, 28]
	Week 5	N/A	[29, 35]
	Week 6	N/A	[36, 42]
NRS reported at study visits	Baseline	1	Before first dose of study drug
PGIC			
	Day 7	7	[1*, 14]
	Week 3	22	[15, 32]
	Week 6	43	[33, 57]
	Safety Follow-up Visit	N/A	Follow the individual visit window to be mapped to individual visits if measured before / on Day 57 or remain as SFU if otherwise.

1* only include day 1 post-dose measurements.

¹ Visit name for analysis purpose is used to report data in tables and figures.

²Only include 7 day measurements before the randomization day.

Notes:

The analysis visit windows will be applied using the following rules for both scheduled and unscheduled visits:

1. If no numerical measurement is available within a visit window, the measurement will be considered missing for the visit.
2. If there is more than 1 numerical measurement available within the same visit window, use the following rules:
 - a. a. For efficacy assessments: if there are multiple measurements within a visit window,
 - i. The measurement closest to the target day will be used; or
 - ii. If there are multiple measurements within the same distance from the target day, the latest measurement will be used.
 - b. For safety assessments: if there are multiple measurements within a visit window,

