 - i. The measurement closest to the target day will be used; or
 - ii. If there are multiple measurements within the same distance from the target day, the latest measurement will be used.
3. When define efficacy and safety at baseline, refer to the generic baseline definition in Section 9.1. If the first dose time is missing, baseline will be defined as the most recent nonmissing measurement collected before the date of the first dose of study drug. For vital sign, there is no time collected and Day 1 will be baseline. For CSSR-S, baseline will be defined as the most recent nonmissing measurement collected before/on Day 1.
4. If the first dose time is missing, use the first dose date to determine post-dose measurements.

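### The Day 7 by-visit QTcF summary normally takes the last, sub-threshold repeat ECG in place of a prolonged scheduled reading

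*Protocol*

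**What the plan says.** **Repeat procedure (Protocol 11.6.4).** The trigger is worded "If the QTcF is increased by >60 msec from the baseline or an absolute QTcF value is ≥500 msec for any scheduled ECG". Two more ECGs then follow a few minutes apart. The next step is conditional: "If either of the QTcF values from these repeated ECGs remains above the threshold value", then "a single ECG will be repeated at least hourly until QTcF values from 2 successive ECGs fall below the threshold value" responsible for the repeats.

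**Handling of extra readings (SAP 9.1).** Measurements from unscheduled visits are used "In scheduled visit windows per specified visit windowing rules". They also enter the maximum and minimum on-treatment values and changes.

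**Choice within a window (SAP Appendix A).** "The analysis visit windows will be applied using the following rules for both scheduled and unscheduled visits". For safety data the first rule is "The measurement closest to the target day will be used". The tie-break is "If there are multiple measurements within the same distance from the target day, the latest measurement will be used". Windows and targets are expressed in study days. For the 12-lead ECG, Table 12-1 has three rows: baseline, Day 7 (post-dose Day 1 through Day 57) and Safety Follow-up.

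**Output (SAP 9.4.3).** "A summary of raw values and change from baseline values will be provided by treatment at each scheduled visit during the TE period", QTcF included. The same section tabulates the maximum on-treatment QT/QTcF value and change in categories, and lists readings that meet the Appendix D criteria.

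**The concern.** The tie-break is generic: the safety rule has the same wording as the efficacy rule. It is harmless where same-day repeats are unrelated to the result. For QTcF they are not. Additional ECGs are prompted by a high reading and stop once readings are low, so keeping the latest one selects on the outcome. A low or ordinary reading sets off no such repeats and is left alone.

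Day 7 is the only on-drug ECG row, so no other by-visit row shows what was displaced. Within an arm the effect is always downward. If triggers are more frequent on VX-150 than on placebo, the difference between arms in this summary shrinks as well.

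**Working it through.** The documents give no figure for this point, so there is nothing of the plan's to reproduce. The check traces the rules and then sizes the effect.

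**1. How a completed series ends.**
- Neither confirmatory ECG above threshold: the last confirmatory ECG is below it.
- Either one above: ECGs continue until two in a row are below, so the last is below.

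**2. Which reading is kept.** Repeats may be stored as unscheduled or under the visit; Appendix A covers both. All ECGs on one study day are the same number of days from Day 7. They tie, and the latest is kept. SAP 9.4.3 makes no exception for ECGs.

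**3. Simulation of the rules.** Assumptions, none from the documents: true change +65 msec, measurement SD 10 msec, first ECG at 10:00, visit on Day 6, 7 or 8, and QTcF declining by 0.5 to 4 msec per hour. Only the >60 msec trigger was modelled.

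| Decline (msec/h) | Series crossing midnight | Kept value at or below trigger, Day 6 visit | Same, Day 7 or 8 visit | Mean drop (msec) |
|---|---|---|---|---|
| 4 | 0% | 100% | 100% | 22.2 |
| 1 | 1.7% | 100% | 99.4% | 18.4 to 18.5 |
| 0.5 | 11.4% | 100% | 93.4% | 16.5 to 17.6 |

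Every series completed the same day gave a sub-threshold value, as step 1 requires. The maximum-on-treatment rule kept the triggering value in 100% of series.

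**4. Shift in the arm mean.** Shift = k × d / N, where k is the number of triggered subjects, d the drop per subject (assumed 5 to 30 msec) and N the arm size. N = 57 is 114/2, the planned maximum; N = 45 is the largest evaluable number in the power table; N = 31 is 62/2, the planned minimum.

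| N | k = 1 | k = 3 |
|---|---|---|
| 57 | 5/57 = 0.09 to 30/57 = 0.53 | 15/57 = 0.26 to 90/57 = 1.58 |
| 45 | 5/45 = 0.11 to 30/45 = 0.67 | 15/45 = 0.33 to 90/45 = 2.00 |
| 31 | 5/31 = 0.16 to 30/31 = 0.97 | 15/31 = 0.48 to 90/31 = 2.90 |

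With k = 0 the shift is zero.

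**5. Maximum and SD with one triggered subject.** Assumed example, N = 57: the other 56 subjects have mean change 10 and SD 14, and the triggered subject's +70 is replaced by +50.
- Scheduled reading: variance = [55 × 14² + (56/57) × 60²] / 56 = (10,780 + 3,537) / 56 = 255.7, so SD = 16.0.
- Latest repeat: variance = [10,780 + (56/57) × 40²] / 56 = (10,780 + 1,572) / 56 = 220.6, so SD = 14.9.
- Mean shift: 20/57 = 0.35 msec.
- That subject's contribution to the maximum falls from +70 to +50.

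**The case against.** **The signal is kept where QT risk is usually read.** This stands. Unscheduled ECGs feed the maximum-on-treatment categories, the listing shows all visits for any subject who meets a criterion, and clinically significant ECG abnormalities are recorded as AEs. A reader might infer that prolongation is hidden from the report; the documents do not support that. Nor would the by-visit and maximum tables contradict each other. They answer different questions, and SAP 9.1 expressly sends unscheduled values to the maximum.

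**It does not happen to every triggered subject.** This also stands. A reader might infer that each triggering value is replaced, or that the by-visit maximum change can never exceed the trigger. Three cases break this:
- A series that crosses midnight on a Day 7 or Day 8 visit can leave an above-threshold reading in place.
- A subject can meet both triggers, and Protocol 11.6.4 does not say which threshold then ends the series. With baseline 430, a reading of 505 (+75) falling to 498 is below 500 but still +68.
- An early-termination ECG after Day 7 loses its place to the closer Day 7 ECG, not to its own repeats.

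**The effect may be nil.** The documents give no expected number of triggers. With 57 per arm, single-ECG SD 10 msec, a decline of 1 msec per hour and no outlying subjects, a simulation gave 0.009 triggers per arm and a shift of 0.005 msec. With 5% of subjects truly at +60 and the rest at +10, the shift was 0.52 msec. The standard error of that arm mean is about √(2 × 10² + 50² × 0.05 × 0.95) / √57 = 17.9/7.55 = 2.4 msec.

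**Data capture is not visible.** The chain needs the repeats and their times in the database. Protocol 11.6.4 mentions printouts kept with source documents, and the eCRF guidelines are not available here.

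None of this supplies a reason for the tie-break, or makes it neutral when a series is completed and recorded.

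**Conclusion.** Wrong as written, minor severity. Followed exactly, the SAP normally puts a sub-threshold repeat into the Day 7 QTcF row for a subject whose scheduled ECG triggered repeats. This holds when the series ends the same day and the repeats are recorded. Because only high readings are replaced, the by-visit mean, SD and maximum are biased toward no effect.

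For the mean, the bias is zero without triggers and about 0.1 to 0.5 msec for one triggered subject in an arm of 57. It reaches about 2 msec only if several trigger (three in an arm of 45 at the largest assumed drop; 2.9 msec at the minimum enrolment of 31 per arm). The maximum and SD can change with a single subject. The numbers of triggered subjects and the drops of 5 to 30 msec are assumptions. The point concerns one descriptive row; no hypothesis test or decision rule depends on it.

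**What to change.** Add an ECG rule to SAP Appendix A: the by-visit ECG summary uses the scheduled (first) ECG of the visit for all subjects, and confirmatory and hourly repeat ECGs enter only the maximum-on-treatment derivation and the listings.

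Averaging the scheduled ECG with its two confirmatory ECGs is not an adequate substitute. It would apply only to triggered subjects, so they would still be treated differently and a small downward bias would remain (0.10 to 0.20 msec in simulation).

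The cost is one sentence and a small programming change, with no new data. The by-visit QTcF figures may look slightly less favourable. The change should be made before database lock and unblinding, so that the choice of reading is not post hoc. The clinical repeat procedure in Protocol 11.6.4 is unchanged.
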